[Part 5 of 7 of the document. The other parts are not shown.]

29. Persistent systolic blood pressure (BP) >165 mmHg or <90 mmHg and diastolic BP >100 mmHg or <60 mmHg at Screening
30. History of cardiac arrhythmias. Subjects with other heart diseases (eg, ischemic heart disease, clinically significant valvular heart disease) that are not stably and adequately controlled, or uncompensated heart failure (New York Heart Association Class III and Class IV)
31. Type 1 or Type 2 diabetes mellitus that is not well controlled
32. Malignant neoplasms within 5 years before Screening (except for basal or squamous cell carcinoma in situ of the skin, or localized prostate cancer that did not require systemic therapy; these do not exclude the subject). Subjects who had malignant neoplasms but who have had at least 5 years of documented evidence of no active disease before Screening need not be excluded.
33. Medical conditions (eg, cardiac, respiratory, gastrointestinal, renal disease) that are not stably controlled, or which, in the opinion of the investigator(s), could affect the subject's safety or interfere with the study assessments
34. Hypopigmentation conditions (eg, albinism and vitiligo). Diagnosis of an underlying disease causing hypopigmentation is not necessary for exclusion if the clinical presentation is consistent with such a condition. Hypopigmentation associated with scarring need not be exclusionary. (revised per Amendment 02)
35. Known or suspected history of drug or alcohol dependency or abuse within 2 years before Screening, current use of recreational drugs or a positive urine drug test at Screening. Subjects who test positive in the urine drug screen need not be excluded if in the clinical opinion of the investigator, this is due to the subject taking prior/concomitant medications for a medical condition that is not exclusionary and not due to drug abuse.
36. Has a "yes" answer to the C-SSRS suicidal ideation questions 4 or 5, or any suicidal behavior assessment within 6 months before Screening, at Screening, or at the Baseline Visit; or has been hospitalized or treated for suicidal behavior in the past 5 years before Screening
37. Violations of the medical restrictions as specified in the Concomitant Medications section of the protocol
38. Planned surgery that requires general, spinal, or epidural anesthesia that would take place during the study. Planned surgery, which requires only local anesthesia and which can be undertaken as a day case without inpatient stay postoperatively, need not result in exclusion if in the opinion of the principal investigator this operation does not interfere with study procedures and subject safety.
39. Participation in any other interventional clinical study related to cognitive impairment within 6 months before Screening unless it can be documented that the subject was in a placebo treatment arm
40. Currently enrolled in another clinical study or used any investigational drug or device within 60 days or 5 half-lives of the investigational medication (whichever is longer) preceding informed consent
41. Hypersensitivity to the study drug or any of the excipients or to other BACE inhibitors, or to the PET tracer, or components of its formulation

42. Females who are lactating or pregnant (as documented by a positive beta-human chorionic gonadotropin [β -hCG] or human chorionic gonadotropin [hCG] test with a minimum sensitivity of 25 IU/L or equivalent units of β -hCG or hCG) at Screening or Baseline. A separate baseline assessment is required if a negative screening pregnancy test was obtained more than 72 hours before the first dose of study drug.

43. Females of childbearing potential who:

- Had unprotected sexual intercourse within 30 days before study entry or who do not agree to use a highly effective method of contraception (eg, total abstinence, an intrauterine device, a double-barrier method [such as condom plus diaphragm with spermicide], a contraceptive implant, an oral contraceptive, or have a vasectomized partner with confirmed azoospermia) throughout the entire study treatment period or for 28 days after study drug discontinuation.
- Are currently abstinent, and do not agree to use a double-barrier method (as described above) or refrain from sexually active during the study treatment period or for 28 days after study drug discontinuation.
- Are using hormonal contraceptives but are not on a stable dose of the same hormonal contraceptive product for at least 4 weeks before dosing or who do not agree to use the same contraceptive during the study treatment period or for 28 days after study drug discontinuation.

(NOTE: All females will be considered to be of childbearing potential unless they are postmenopausal [amenorrheic for at least 12 consecutive months, in the appropriate age group, and without other known or suspected cause] or have been sterilized surgically [ie, bilateral tubal ligation, total hysterectomy, or bilateral oophorectomy, all with surgery at least 1 month before dosing]).

44. Males who have not had a successful vasectomy (confirmed azoospermia) or they and their female partners do not meet the criteria above (ie, not of childbearing potential or not practicing highly effective contraception throughout the study period or for 28 days after study drug discontinuation). No sperm donation is allowed during the study period and for 28 days after study drug discontinuation.

9.3.3 Removal of Subjects from Therapy or Assessment

The investigator may discontinue study drug or withdraw the subject from the study at any time for safety or administrative reasons. The subject may decide to stop study drug or withdraw from the study at any time for any reason.

Subjects who discontinue taking study drug prematurely for any reason will undergo an ED Visit within 7 days of their last dose of study drug (see [Section 9.1.2.2](#)). Follow-Up Visits will also be scheduled 4 and 12 weeks after the last dose of study drug (see [Section 9.1.2.3](#)).

Subjects who discontinue study drug prematurely will also be scheduled to return to the study site for each scheduled visit when clinical efficacy assessments are to be conducted (ie, at Visits 11, 14, 15, 16, 17, and 18, if these visits have not already been performed). At these visits, only clinical efficacy assessments (MMSE, CDR, ADAS-cog₁₄, FAQ, CBB and ISLT) will be conducted. Regularly scheduled clinical efficacy visits do not need to be attended if they fall within 8 days (visit window) after the Early Discontinuation Visit or within \pm 8 days

of either of the Follow-Up Visits (Visit 19 and Visit 20). Subjects who discontinue early from study drug are considered on study as long as they return for their regularly scheduled clinical efficacy visits as outlined above.

The primary reason for discontinuation and all other reason(s) contributing to the subject's discontinuation from study drug(s) should be collected on the Subject Disposition eCRF page. In addition, the date of last dose of study drug(s) will be recorded on the Study Drug Dosing eCRF page. If a subject discontinues study drug and withdraws from the study at the same time, the ED Visit will be followed (see [Section 9.5.5](#)).

Safety-related criteria for discontinuation of study drug include the following:

- a. A study drug discontinuation threshold will be set based on absolute counts of CD4 (T helper cells), CD8 (cytotoxic T cells), or CD19 (B cells). The discontinuation threshold will be set at below the level of the population-adjusted LLN (CD4=396 cells/ μ L; CD8=157 cells/ μ L; and CD19=74 cells/ μ L), at a level that represents a greater risk of opportunistic infection in the treated population. (revised per Amendment 02) For CD4 (T helper cells) the discontinuation threshold is 250 cells/ μ L. For CD8 (cytotoxic T cells) and CD19 (B cells) the discontinuation thresholds are 150 cells/ μ L and 50 cells/ μ L, respectively. Any subject who has CD4 (T helper cells), CD8 (cytotoxic T cells), or CD19 (B cells) absolute counts below the discontinuation threshold as confirmed by a repeat test conducted within 1 week of the initial test will be discontinued from study drug.
- b. Subjects with CD4 (T helper cells), CD8 (cytotoxic T cells), or CD19 (B cells) absolute counts between the population-adjusted LLN and the discontinuation threshold will have lymphocyte subset counts performed on a weekly basis. (revised per Amendment 02) Subjects with a >33% reduction from baseline in CD4 (T helper cells), CD8 (cytotoxic T cells), or CD19 (B cells) absolute counts will also have lymphocyte subset counts performed on a weekly basis. During the early stages of the treatment period, where visits are conducted weekly (ie, Visits 4, 5, 6, and 7), lymphocyte subsets are already scheduled to be measured on a weekly basis and so additional visits or blood draws are not required. (revised per Amendment 02) For these subjects, the decision as to whether the subject remains on study drug or is to be discontinued from study drug will be based upon clinical judgment and will take into account any clinical presentation in addition to the lymphocyte subset counts. These subjects may continue with treatment if there is no clinical evidence of infection. They will be discontinued from study drug if they have infections of a moderate to severe intensity (eg, subjects whose infections are not localized, or are systemically unwell, or who require systemic anti-infective drug treatment).

Table 1 Study Drug Actions for Lymphocyte Subset Absolute Counts

| Lymphocyte subset absolute counts | Action | Decision to continue or discontinue |
|--|--|---|
| CD4 (T helper cells), CD8 (cytotoxic T cells), or CD19 (B cells) absolute counts below discontinuation threshold | Retest within 1 week along with CBC with differentials | If retest performed within 1 week confirms lymphocyte subset counts below the discontinuation threshold, discontinue study drug |
| CD4 (T helper cells), CD8 (cytotoxic T cells), or CD19 (B cells) absolute counts between population-adjusted LLN and discontinuation threshold or >33% reduction from baseline in CD4 (T helper cells), CD8 (cytotoxic T cells), or CD19 (B cells) absolute counts | Lymphocyte subset counts (and CBC with differentials) to be performed weekly until lymphocyte subset counts return to \geq population-adjusted LLN or no more than 33% reduction from baseline | Decision will be based upon lymphocyte subset counts and clinical judgment |

LLN = lower limit of normal, CBC = complete blood count. (table revised per Amendment 02)

- c. Subjects with clinical evidence of infection will have their CD4 (T helper cells), CD8 (cytotoxic T cells), and CD19 (B cells) absolute counts measured. Blood and other biological samples will also be collected for investigations of infective pathogens (eg, serological tests, quantitative polymerase chain reaction, microscopy, and culture) where appropriate. In subjects with infection, if any of their absolute cell counts meets the discontinuation thresholds, study drug will be discontinued. All subjects with severe infections will be discontinued from study drug. All subjects with herpes zoster (shingles) or ocular herpes infections will be discontinued from study drug, regardless of severity of presentation. Subjects with mild or moderate infection may continue treatment with study drug unless otherwise clinically indicated or otherwise specified below. Specifically, when any of the CD4 (T helper cells), CD8 (cytotoxic T cells), and CD19 (B cells) absolute counts are between the population-adjusted LLN and the discontinuation thresholds or have shown >33% reduction from baseline, subjects with infections of moderate intensity will be discontinued from study drug (eg, subjects whose infections are not localized, or subjects who are systemically unwell, or who require systemic anti-infective drug treatment). All subjects with infection who are discontinued from study drug will be followed for a period of 12 weeks or until the infection resolves/stabilizes or until the CD4 (T helper cells), CD8 (cytotoxic T cells), and CD19 (B cells) absolute counts have returned to greater than population-adjusted LLN (whichever comes latest). (revised per Amendment 02)

Table 2 Study Drug Actions for Lymphocyte Subset Absolute Counts and Infection

| Criterion | Severity of Infection | | | |
|--|---|---|---|------------------------|
| | None | Mild | Moderate | Severe |
| CD4 (T helper cells), CD8 (cytotoxic T cells), or CD19 (B cells) absolute counts below discontinuation threshold | If confirmed with repeat testing within 1 week, then discontinue study drug. | Discontinue study drug | Discontinue study drug | Discontinue study drug |
| CD4 (T helper cells), CD8 (cytotoxic T cells), or CD19 (B cells) absolute counts between population-adjusted LLN and discontinuation threshold or >33% reduction from baseline in CD4 (T helper cells), CD8 (cytotoxic T cells), or CD19 (B cells) absolute counts | May continue treatment with study drug unless discontinuation is clinically indicated | May continue treatment with study drug unless discontinuation is clinically indicated | Discontinue study drug | Discontinue study drug |
| CD4 (T helper cells), CD8 (cytotoxic T cells), or CD19 (B cells) absolute counts always > population-adjusted LLN and no reduction from baseline >33% | May continue treatment with study drug unless discontinuation is clinically indicated | May continue treatment with study drug unless discontinuation is clinically indicated | May continue treatment with study drug unless discontinuation is clinically indicated (See (e) for exception) | Discontinue study drug |

LLN = lower limit of normal. Table revised per Amendment 02

- d. A subject with any skin rash of moderate to severe intensity, or any rash lasting more than 72 hours regardless of severity (see (e) for exception), will be discontinued from study drug and a dermatological consult will be requested regardless of whether the rash is considered drug-related or due to other causes. For cases where the investigator suspects a drug rash, regardless of severity, the subject will be discontinued from study drug, a dermatological consult will be requested, and a skin biopsy will be performed to confirm the diagnosis. The skin rash will be treated as per standard care and will be followed up until resolution regardless of etiology or severity.
- e. Subjects who develop moderate to severe oral or genital herpes should be discontinued from study drug. Subjects who develop a mild case of oral or genital herpes may remain on study drug even if the event lasts more than 72 hours.
- f. Development of any of the following features on MRI: vasogenic edema, macrohemorrhage, an area of superficial siderosis, or a symptomatic microhemorrhage. If discontinued from study drug, subjects will undergo an ED Visit within 7 days after discontinuation and will attend the Follow-Up Visits 4 and 12 weeks after the last dose of study drug. They will also undertake an Unscheduled Visit (with MRI) at approximately 4 weeks after the visit at which such MRI features were first identified. An MRI will also be performed at approximately the time of the second Follow-Up Visit (Visit 20). Additional visits for safety may be arranged if clinically indicated in the opinion of the investigator, including after 12 weeks after the last dose of study drug. At any time during the treatment period, subjects who have asymptomatic, treatment-emergent microhemorrhages as detected by MRI, but none of the features which merit discontinuation of treatment (ie, vasogenic edema, macrohemorrhage, an area of

superficial siderosis, or a symptomatic treatment-emergent microhemorrhage) may continue with treatment. These subjects will have safety assessments (including MRI) at approximately 4 weeks after the visit at which such MRI features were found. They will also continue with the scheduled MRI scans. Additional unscheduled MRI scans may be arranged on an individual subject basis in discussion with the study medical monitor.

- g. A postdose ECG with an average QTcF interval >500 msec from triplicate ECGs
- h. A postdose ECG with a QTcF interval increase from baseline >60 msec and a QTcF interval >450 msec as demonstrated from triplicate ECGs
- i. Any seizure (motor or non-motor)
- j. Pregnancy

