|-----------------|------------------|-------------------|------------------|------------------|-------------------|
| n | 50 | 93 | 30 | 30 | 203 |
| Mean | 213.47 | 198.49 | 159.20 | 172.77 | 192.57 |
| Median | 189.66 | 163.00 | 118.50 | 159.50 | 164.86 |
| 5th percentile | 84.81 | 59.00 | 38.00 | 69.00 | 59.00 |
| 10th percentile | 102.26 | 81.00 | 42.00 | 70.50 | 74.00 |
| 25th percentile | 139.66 | 104.00 | 75.00 | 100.00 | 104.58 |
| 75th percentile | 261.51 | 225.00 | 225.00 | 246.00 | 246.00 |
| 95th percentile | 376.67 | 443.00 | 424.00 | 384.00 | 402.00 |
| Range | 66.19, 593.48 | 17.00, 1066.00 | 37.00, 455.00 | 39.00, 415.00 | 17.00, 1066.00 |

Table 11 Summary of CD Counts (Parameter: CD8)

| | BEAM 002 | BEAM 202 | Pilot AD/MCI | Pilot Control | Combined Total |
|-----------------|------------------|------------------|------------------|-------------------|-------------------|
| n | 50 | 93 | 30 | 31 | 204 |
| Mean | 362.72 | 352.18 | 324.63 | 427.74 | 362.20 |
| Median | 364.74 | 330.00 | 344.00 | 315.00 | 336.39 |
| 5th percentile | 115.02 | 138.00 | 86.00 | 100.00 | 115.02 |
| 10th percentile | 170.24 | 151.00 | 159.50 | 153.00 | 157.00 |
| 25th percentile | 253.37 | 213.00 | 204.00 | 217.00 | 230.00 |
| 75th percentile | 465.52 | 425.00 | 405.00 | 494.00 | 438.00 |
| 95th percentile | 614.57 | 716.00 | 557.00 | 988.00 | 702.00 |
| Range | 98.45, 702.50 | 37.00, 803.00 | 61.00, 702.00 | 54.00, 2255.00 | 37.00, 2255.00 |

Table 12 Summary of CD Counts (Parameter: CD4)

| | BEAM 002 | BEAM 202 | Pilot AD/MCI | Pilot Control | Combined Total |
|-----------------|--------------------|--------------------|--------------------|--------------------|--------------------|
| n | 50 | 93 | 30 | 31 | 204 |
| Mean | 846.15 | 839.58 | 789.27 | 804.52 | 828.46 |
| Median | 836.94 | 805.00 | 777.50 | 771.00 | 791.50 |
| 5th percentile | 388.44 | 337.00 | 395.00 | 351.00 | 344.00 |
| 10th percentile | 479.55 | 361.00 | 490.00 | 427.00 | 396.00 |
| 25th percentile | 639.54 | 620.00 | 661.00 | 669.00 | 633.77 |
| 75th percentile | 1031.49 | 1078.00 | 924.00 | 1014.00 | 1039.50 |
| 95th percentile | 1315.55 | 1404.00 | 1124.00 | 1327.00 | 1347.00 |
| Range | 274.90, 1643.55 | 197.00, 1481.00 | 248.00, 1720.00 | 143.00, 1336.00 | 143.00, 1720.00 |

References:

1. Yan et al., Immunity and Ageing 2010 v. 7:4; The effect of ageing on human lymphocyte subsets: comparison of males and females.

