 - c. Cutaneous manifestations of immunological disease that do not require systemic immunosuppressive therapy or systemic immunomodulatory therapy need not be excluded (topical steroid treatment is permitted).
22. CD4 (T helper cells), CD8 (cytotoxic T cells), or CD19 (B cells) absolute counts below population-adjusted LLN at Screening or Baseline and confirmed by a repeat test conducted 1 week after the initial test. The population-adjusted LLN for CD4 (T helper cells), CD8 (cytotoxic T cells), and CD19 (B cells) absolute counts are 396, 157, and 74 cells/ μ L respectively. See [Appendix 5](#). (revised per Amendment 02)
23. Ig (IgG, IgA, or IgM) levels below the LLN at Screening or Baseline, unless both the Investigator and the Medical Monitor agree that the finding is not clinically significant. The assessment of clinical significance will include, but not be limited to, evidence of clinical immunodeficiency. The discussion with the Medical Monitor should include a detailed review of medical history of infections, clinical and laboratory findings. (revised per Amendment 01)
24. Clinically significant deviation from normal in physical examination, vital signs, or clinically laboratory tests at Screening or Baseline
25. A prolonged QT/ corrected QT interval (QTc) interval (QTc >450 msec) at Screening or Baseline as demonstrated by average QTc interval from triplicate ECGs. A history of risk factors for torsade de pointes (eg, heart failure, hypokalemia, family history of long QT Syndrome) or the use of concomitant medications that prolong the QT/QTc interval.
26. Any other abnormality of the ECG at Screening or Baseline (including QRS >110 msec, abnormal electrical axis, PR interval >220 msec and conduction abnormalities) considered clinically significant by the investigator
27. Left bundle branch block at Screening or Baseline
28. Persistent heart rate <50 or >100 beats per minute (bpm) at Screening or Baseline

29. Persistent systolic blood pressure (BP) >165 mmHg or <90 mmHg and diastolic BP >100 mmHg or <60 mmHg at Screening
30. History of cardiac arrhythmias. Subjects with other heart diseases (eg, ischemic heart disease, clinically significant valvular heart disease) that are not stably and adequately controlled, or uncompensated heart failure (New York Heart Association Class III and Class IV)
31. Type 1 or Type 2 diabetes mellitus that is not well controlled

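### Table 1's stop rule for weekly lymphocyte counts uses 'or', so a subject with both triggers can meet it while item (b), and the row's own entry condition, still call for weekly counts

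*Protocol*

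**What the plan says.** Section 9.3.3, item (b), gives two triggers for weekly counts. The first covers subjects in the band below the LLN: "absolute counts between the population-adjusted LLN and the discontinuation threshold will have lymphocyte subset counts performed on a weekly basis". The second covers subjects whose CD4, CD8 or CD19 count has fallen more than 33% from baseline, whose "absolute counts will also have lymphocyte subset counts performed on a weekly basis". Item (b) has no stopping rule of its own.

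Table 1, second row, merges the two. Its first column admits a subject who meets either condition. Its action column asks for weekly subset counts (with a complete blood count) until they return to at least the "population-adjusted LLN or no more than 33% reduction from baseline". Its third column leaves the decision on study drug to the counts and clinical judgment.

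Table 2, third row, defines the unaffected state with the same two conditions joined the other way: "absolute counts always > population-adjusted LLN and no reduction from baseline >33"%.

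Section 9.3.3 appears twice in the document, and Table 1 has the same wording in both places.

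**The concern.** Entry on either of two conditions implies exit only when neither holds. Table 1 instead lets either exit condition suffice. A subject with both triggers can therefore satisfy the stop clause with one trigger unresolved, at the moment when item (b) and the row's first column both ask for weekly counts. The action table that a site is likely to work from then disagrees with itself and with the text it summarises.

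Lymphocyte reduction is the drug's identified risk (Section 7.1), and Section 9.2.6 gives the move from 14 days to 18 months of dosing as the reason for the safety measures. What is at stake is the interval between counts in a subject who has not fully recovered. No endpoint, error rate, power figure or estimate depends on it.

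**Working it through.** **Inputs.** LLNs and discontinuation thresholds are from Section 9.3.3, item (a). Pooled percentiles are the combined columns of Appendix 5, Tables 10 to 12. The plan states no figure of its own on this point to reproduce.

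**Step 1: when does a count below the LLN also trip the 33% trigger?** A count equal to the LLN is exactly a 33% fall when baseline = LLN / 0.67. Above that baseline, any count below the LLN is also a fall of more than 33%.

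| Subset | LLN | Threshold | LLN / 0.67 | Pooled 25th pct. | Pooled median | Fall at the LLN from median |
|---|---|---|---|---|---|---|
| CD4 | 396 | 250 | 591.0 | 633.77 | 791.50 | 50.0% |
| CD8 | 157 | 150 | 234.3 | 230.00 | 336.39 | 53.3% |
| CD19 | 74 | 50 | 110.4 | 104.58 | 164.86 | 55.1% |

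**Step 2: how common are such baselines in the pooled sample?**
- CD4: 633.77 exceeds 591.0, so at least 75% lie above the break-even.
- CD8: 234.3 lies between the 25th percentile and the median, so 50% to 75%. By linear interpolation, 25 + 25 × (234.3 − 230.00) / (336.39 − 230.00) = 26.0% lie below, so about 74% above.
- CD19: also 50% to 75%. By interpolation, 25 + 25 × (110.4 − 104.58) / (164.86 − 104.58) = 27.4% lie below, so about 73% above.

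Exclusion criterion 22 removes subjects with "absolute counts below population-adjusted LLN at Screening or Baseline and confirmed by a repeat test", and each LLN is the pooled 10th percentile. If enrolled baselines otherwise follow the pooled sample (an assumption), the shares become at least 75/90 = 83% for CD4, and 50/90 = 56% to 75/90 = 83% for CD8 and CD19.

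**Step 3: apply both rules to a recovering subject.**
- CD4, baseline 633.77. At 380, below the LLN and down 1 − 380/633.77 = 40.0%: both triggers active. At 400, above the LLN but down 1 − 400/633.77 = 36.9%: stop clause met, item (b) still active.
- CD8, baseline 336.39. At 152, between 150 and 157 and down 54.8%: both active. At 160, above the LLN but down 52.4% and only 10 cells above the discontinuation threshold: stop clause met, item (b) still active.

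Below the break-even baseline the order reverses. With an illustrative CD4 baseline of 580, a count of 380 is down 34.5% and below the LLN. At 392 it is down 32.4%, so the 33% limb has cleared, but it is still below 396.

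**Step 4: width of the conflict.** With a baseline at the pooled median, the two rules disagree from the LLN up to 0.67 × baseline: 396 to 530 (CD4), 157 to 225 (CD8) and 74 to 110 (CD19) cells/µL.

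**Step 5: the gap if weekly counts stop.** Table 7 schedules counts at Weeks 26, 39, 52, 65 and 78, so after Week 26 the interval is 13 weeks.

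**Step 6: the corrected exit.** With 'and', a CD4 baseline of 800 gives: continue at 380; continue at 400 (50.0% down); continue at 500 (37.5% down); stop at 540 (32.5% down). Weekly counts then last exactly as long as an item (b) trigger is active.

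**The case against.** The strongest answer is that Table 1 recaptures the subject. Someone still down more than 33% continues to meet the second row's first column, whose action is weekly counts. Reading the exit trigger by trigger is also natural: a count cannot return to a limit it never left, and on that reading a subject with two triggers continues until both clear. Item (b) and the 'and' in Table 2 point to the same intent.

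Much of this stands. The clause permits early stopping; it does not compel it, and a careful site would continue. But recapture does not remove the conflict: the same row would tell the site both that it may stop and that it must go on. Table 1 has no word such as respectively or as applicable. Item (c), which also lists alternatives with 'or', does say that the latest of them governs; Table 1 does not.

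Two stronger readings may tempt a reader. One is that the row is void even for a single trigger: CD4 falling from 800 to 500, or from 450 to 390, literally meets the stop clause at once. The verb 'return' makes the trigger-by-trigger reading plausible there, so the point does not rest on that case. The other is that the shares in the working count affected subjects. They count only baselines at which the two triggers coincide. The pooled sample also includes 81 of 204 people (CD4 and CD8 tables) from healthy elderly cohorts, and Section 9.4.4 reports a mean CD4 change of only −3.1% after 14 days at 100 mg, a dose with higher exposure than this trial's top dose.

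Other safeguards also apply: denser scheduled counts up to Week 26, counts in any subject with infection (item c), unblinded DSMB review, blinded sponsor monitoring and unscheduled visits.

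**Conclusion.** The point holds as an internal contradiction in a safety-monitoring rule. For a subject with both triggers, Table 1's stop clause can be met while item (b) and the row's own entry condition require weekly counts. That combination is the usual form of a below-LLN count at the baselines in Appendix 5, if enrolled subjects resemble that pooled sample.

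Severity is low. The discontinuation thresholds and all efficacy analyses are untouched. How many subjects will reach a trigger cannot be derived, because the document gives no within-subject variability; nor can the number whose site would stop early, or any resulting harm. The documents do not support saying that the protocol instructs sites to stop, or that most subjects are exposed. They support saying that sites could apply the row differently, with up to 13 weeks to the next scheduled count after Week 26. The correction is worth making because it is one clause in a rule guarding the drug's known risk.

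**What to change.** In both copies of Table 1, change the second-row exit to: until CD4, CD8 and CD19 counts are all at or above the population-adjusted LLN and none shows more than a 33% reduction from baseline. Counts below the discontinuation threshold stay under the first row. The exit then matches item (b) and Table 2.

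The only cost is draws that item (b) already requires. By Table 8 each takes 4 mL for subsets plus 5 mL for hematology, 9 mL in all. Between two visits 13 weeks apart that is at most 12 extra draws, 12 × 9 = 108 mL. In the extreme case of a subject affected for all 78 weeks, 78 weekly counts less the 15 scheduled on treatment leaves 63 extra draws, 63 × 9 = 567 mL, against a scheduled whole-study blood total of 402 mL. If that burden is thought too high, item (b) should be relaxed openly, not through the wording of Table 1.

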9.1.2.1 Treatment Period

Subjects will be randomized at the beginning of the Treatment Period and will receive study drug or placebo, to be administered orally QD with food. Double-blinding to study drugs will be in effect throughout the Treatment Period. The dose for a subject will not be changed during the study. However, dose adjustment for Stage B may be considered and subjects already randomized to a dose that needs to be adjusted will be switched to continue their treatment at the new adjusted dose.

Safety criteria for discontinuation of study drug are detailed in [Section 9.3.3](#).

Subjects will attend the study site every week for the first 4 weeks after beginning study drug, then fortnightly until 12 weeks have elapsed since first dose. Visits will then be conducted at 16, 20, 26, 39, 52, 65, and 78 weeks after the first dose.

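### Table 1 of section 9.3.3 lets weekly lymphocyte testing end for a subject who has breached both limits once only one of them has recovered

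*Protocol*

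**What the plan says.** Protocol section 9.3.3, text (b), sets two separate triggers for weekly testing. Subjects with "absolute counts between the population-adjusted LLN and the discontinuation threshold will have lymphocyte subset counts performed on a weekly basis"; and subjects whose count has fallen more than 33% from baseline in "absolute counts will also have lymphocyte subset counts performed on a weekly basis" form the second group. Text (b) does not say when weekly testing ends.

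Table 1 puts both triggers into one row, joined by *or*. Its action column gives the only end rule: weekly until the counts return to at least the "population-adjusted LLN or no more than 33% reduction from baseline".

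Table 2 uses the same two limits to decide what happens at an infection. Its second row covers counts "between population-adjusted LLN and discontinuation threshold or >33% reduction from baseline" and stops study drug at a moderate infection. Its third row, the subject with neither limit breached, joins the two conditions with *and*.

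The LLNs are 396, 157 and 74 cells/µL for CD4, CD8 and CD19. The stopping thresholds are 250, 150 and 50.

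**The concern.** Weekly testing starts on A or B, where A is a count below the LLN (but not below the stopping threshold) and B is a fall of more than 33%. The matching end is neither A nor B. Table 1 instead ends testing when A has cleared or B has cleared. A subject with both can therefore be released while one persists.

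What is at stake is how soon a further fall would be seen. A released subject goes back to the visit schedule, and the stopping thresholds act only on a measured count. Lymphocyte subsets are this protocol's chosen marker for possible immunotoxicity, and the study moves from 14 days of dosing to 18 months. Two sites could also monitor the same subject differently, one acting on the end rule in Table 1 and the other on text (b).

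**Working it through.** **Inputs.** LLNs and stopping thresholds: section 9.3.3 (a). Combined medians, used as example baselines: Appendix 5, Tables 10 to 12 (CD4 791.5, CD8 336.39, CD19 164.86). Combined 25th percentiles from the same tables: 633.77, 230 and 104.58. Visit weeks: section 9.1.2.1. The plan states no figure of its own to reproduce; this is a check of logic with example counts.

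**Step 1: one subject through the rule.** CD4 baseline 791.5.
- Falls to 380: 380 < 396, so the LLN is breached. The fall is 1 − 380/791.5 = 52.0%, so the 33% limit is breached as well. Weekly testing starts on both triggers.
- Rises to 400: 400 ≥ 396, so the count has returned to the LLN and the Table 1 end rule is met. The fall is 1 − 400/791.5 = 49.5%, still more than 33%. The entry column of the same row, text (b) and Table 2 row 2 all still apply.

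The mirror case works through the other limit. CD4 420 to 270 is 1 − 270/420 = 35.7% down and below 396. A rise to 300 is 1 − 300/420 = 28.6% down, which meets the end rule while the count is still below the LLN.

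**Step 2: when is a count below the LLN a double breach?** The 33% limit lies at 0.67 × baseline. If 0.67 × baseline exceeds the LLN, every count below the LLN is also more than 33% down. That holds when baseline > LLN/0.67.

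| Subset | LLN/0.67 | Combined median | Combined 25th percentile |
|---|---|---|---|
| CD4 | 396/0.67 = 591 | 791.5 | 633.77 |
| CD8 | 157/0.67 = 234 | 336.39 | 230 |
| CD19 | 74/0.67 = 110 | 164.86 | 104.58 |

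All three medians exceed the cut-off, so for at least half of that sample a count below the LLN would be a double breach. For CD4 the 25th percentile exceeds it too, so there it is at least three quarters.

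**Step 3: what release means.** Section 9.1.2.1 has visits weekly to week 4 and fortnightly to week 12, and then: "Visits will then be conducted at 16, 20, 26, 39, 52, 65, and 78 weeks after the first dose". Subsets are taken at each of these visits (Table 7). The gaps after week 4 are therefore 2 weeks to week 12, then 4, 4 and 6 weeks to week 26, then 13 weeks to week 78.

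**Step 4: the rule with *and*.** A check of integer counts at example baselines for all three subsets found no count that meets both the entry condition and an end rule written with *and*.

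**The case against.** The best defence is that Table 1 says counts must *return to* a limit, and lists the two end points in the same order as the two triggers. A count that never fell below the LLN cannot return to it. The ordinary reading is then that each trigger ends on its own limit. This stands for a single breach. A reader might infer that a subject with one breach meets the end rule on the very result that started testing; the wording does not support that, and it would make the row cancel itself. It does not settle the double breach, where a CD4 of 400 really has returned to the LLN.

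A second defence is that the released subject still meets the entry column and is caught again at once. That is a fair account of what a careful site would do, and the *and* in Table 2 suggests that it was intended. But it leaves one row saying both stop and continue on the same result.

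A reader might also infer that text (b) and Table 1 state two conflicting end rules. They do not: text (b) states none. The conflict is between the exit in Table 1 and the two entry triggers.

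Third, the consequences are limited. Stopping thresholds are unchanged. Text (c) adds fresh counts at infection ("Subjects with clinical evidence of infection will have their CD4", CD8 and CD19 measured). Unscheduled visits are allowed, and the safety board reviews unblinded data about every 3 months until recruitment ends. In the 14-day multiple-dose study, reductions appeared by Days 8 to 15, inside the period of frequent visits here, and mean CD4 at 100 mg fell by only 3.1%. All of this stands and keeps the point modest. It does not close the gap: text (c) acts only once infection is clinically evident, unscheduled visits depend on the investigator, the clinical judgment in Table 1 concerns continuing drug rather than test frequency, and a mean over 14 days says little about individual falls over 18 months.

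**Conclusion.** The point holds for the double breach. As written, Table 1 permits weekly testing to stop while a subject is still more than 33% below baseline (or, from a low baseline, still below the LLN), although the same row and text (b) call for it to continue. At typical baselines a double breach is the usual form of a count below the LLN, so this is not a corner case among such counts.

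The conclusion assumes that the combined Appendix 5 sample resembles the baselines of enrolled subjects, and that some sites would act on the end rule as worded. The protocol gives no data on how often counts fall this far or on any resulting harm, so no frequency is claimed. It is a minor-to-moderate correction to a safety-monitoring rule, with no bearing on sample size, power or type I error.

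**What to change.** In Table 1, change the action to: lymphocyte subset counts (with CBC and differentials) weekly until CD4, CD8 and CD19 are all at or above the population-adjusted LLN and none is more than 33% below baseline.

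This is one clause. It needs no extra subjects and moves no stopping threshold. The added tests are at most the weekly ones that the triggers in text (b) already call for. If sites already continue until both limits have recovered, practice does not change.
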